The research activities involve a two-arm prospective RCT enrolling a sample of 600 AMSM with the aim of maintaining a randomized sample of approximately 500 online-recruited AMSM (13-18), assuming 15-20% attrition. After consent and completion of the online baseline survey, AMSM are randomized to either the control or experimental condition (Intervention, n=300; Control, n=300). Participants in the control arm will receive access to only the resource locator function of iReach, allowing them to search for local resources. Participants recruited nationally will receive a list of national resources. Participants in the experimental arm will receive access to all iReach functions, including life skills education, goal setting, local/national resource directory, a discussion forum related to life skills and goal setting, and the ability to link to a Peer Mentor through the VSee video-chat function. After consent and a baseline survey, AMSM are randomized to either the attention control or intervention condition. Self-completed study assessments are conducted online every three months across the intervention and attention-control follow-up time points, with a total follow-up period of 12 months for participants initially randomized into the intervention group, and 15 months for participants initially randomized into the control group. In months 12 to 15, we will make the intervention accessible to AMSM in the attention-control condition. The primary outcomes are cognitive (e.g., HIV prevention attitudes, norms, self-efficacy, behavioral intentions); behavioral outcomes are secondary (e.g., condom use, HIV testing, PrEP use). The proposed study design thus tests the impact of an e-delivered life skills intervention with an embedded video-chat peer motivational interviewing function on cognitive and behavioral HIV-related outcomes on a large (n=600) sample of AMSM.

The study is funded for approximately 5 years (Project Period: 07/28/2016 to 02/28/2021). Once consented, participants randomized into the intervention group will be active in the study for 12 months. Participants randomized into the control group will be active in the study for 15 months.

METHODS:

1. Study Instruments:

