pressure from partner; (4) sexual satisfaction and desire; (5) having sex with male, female, and transgender partners; (6) HIV/STIs, and (7) condom use. The existing assessment was developed to focus on the exchanges between mothers and AMSM in a racially and ethnically diverse sample of YMSM. We will extend it to include fathers and/or other trusted adults identified by the AMSM. Motivation to engage in condom use behaviors will be assessed using 3 scales from Fisher et al.s Teen Health Survey. We will measure motivation using 3 scales: attitudes (3 items; .60), social norms regarding peers and partners (6 items; .80), and behavioral intentions (3 items; .80). Motivation to adopt routine HIV testing (e.g., making a calendar for HIV testing or talking to partners about HIV testing) will be assessed with 3 subscales assessing AMSMs attitudes, social norms, and behavioral intentions that we have used in the past with this population. Each attitude item is measured with three five-point semantic differential scales (good-bad; worthless-valuable; pleasant-unpleasant). Social norms assess the extent to which participants felt that friends and family believed he or she should test for HIV on a 1 to 5 scale. Behavioral intentions items assess participants intention to adopt HIV testing, on a 1 (very unlikely) to 5 (very likely) scale. We will measure self-efficacy across three behaviors: condom-use self-efficacy (3 items; =.72), safer-sex negotiation self-efficacy with casual partners (5 items; =.94) and regular partners (5 items; =.91), and discussing HIV testing with partners (3 items; =.90). Finally, we will measure PrEP knowledge, awareness, and use of PrEP. The survey will contain a detailed description of PrEP to orient the participant. Questions related to PrEP uptake (i.e., willingness, awareness) are adapted from recent studies of PrEP attitudes with AMSM. PrEP awareness will be a single item measure of whether the participant has heard of PrEP (binary: yes/no). Among non-PrEP users, PrEP willingness will be measured using an existing 8-item scale (=.84) developed for YMSM (range 1-3) to gauge how willing they would be to use PrEP across different conditions (e.g., partner types; experiencing potential side effects). Secondary Outcomes: We will also examine the interventions efficacy among AMSM who engage in risk behaviors. Specifically, we will assess whether the intervention aided to (1) reduce sexual risk behaviors, (2) decreased ATOD (alcohol, tobacco and other drug) use, and (3) increase linkage to HIV prevention services. For incident HIV+ cases, we will assess AMSMs linkage and retention in care. Sexual risk behavior will be assessed using the Sexual Practices Assessment Schedule for Youths. We have adapted this assessment for use in previous online studies with YMSM. The assessments asks lifetime of sexual partners and types of sexual acts (e.g., kissing, touching, oral sex, penetrative sex) before proceeding any further. For behaviors reported, the assessment then explores the number of occasions of different sexual acts (oral, anal; receptive, insertive) with three different types of partners (romantic interest, casual partner [hookup] or friend with benefits), use of condoms during the past 3 months, and knowledge about partners HIV status. The assessment also differentiates between male and female partners. We will adapt the assessment to ascertain whether, to their knowledge, their sexual partners are on PrEP. HIV/STI testing and care: The baseline survey will include questions on lifetime HIV/STI testing history. Follow-up surveys will repeat the questions from the baseline, and will also include questions on HIV/STI testing in each 3-month period including test results. Among newly diagnosed HIV+ cases, we will assess their linkage and retention in care. We will also assess onset of ART initiation and viral suppression as exploratory indicators, as we recognize that our follow-up period may not be a sufficient amount of time to see these changes. PrEP use: At baseline and each follow-up assessment, we will measure whether eligible AMSM are using PrEP. ATOD (alcohol, tobacco, and other drug) use: We will assess frequency of ATOD use (as measured in National Survey on Drug Use & Health) over the past 3 months and past 30 days for alcohol, cigarettes, tobacco, marijuana, non-prescription drugs, cocaine, amphetamines, depressants, and heroin. We will also ask age of onset. If respondents indicate current smoking behaviors we ask how many cigarettes they smoke daily and past year attempts to quit smoking. If respondents indicate alcohol use, we will ask the Alcohol Use Disorders Identification Test (AUDIT) developed by the WHO. The AUDIT is a 10-item screening questionnaire with 3 questions on the amount and frequency of drinking, 3 questions on alcohol dependence, and 4 on problems caused by alcohol. Self-efficacy for managing triggers for substance use: We will administer a composite measure that assesses self-efficacy for managing triggers for alcohol or other drugs using the Situational Confidence Questionnaire 8 item version (SCQ-8) is a brief, validated measure of self-efficacy for managing internal (e.g., emotional) and external (e.g., situations) triggers for ATOD use. Psychosocial Mediators of Interest: As articulated in Figure 2, we will measure the following psychosocial mediators that result in the hypothesized intervention effects: Life skills will be assessed using several constructs. The Future Goals subscale of the Stanford Time Perspective Inventory assesses the degree to which participants were striving for future goals and rewards. The scale is made up of 13 items (.7032) rated on a 5-point scale (1=very untrue-5=very true). We will also use the Life Outcome Expectancies measure developed by the Adolescent Trials Network. The measure is divided into two conceptual domains, Outcome Expectations and Efficacy. The Life Outcome Expectancies questions measure participants perceived likelihood of reaching life milestones on a five-point scale (1=not at all-5=has already occurred; .70). The Efficacy questions measure participants perceived control over their life circumstances on a 4-point scale (1=poor-4=excellent; .80). Personal competency will be measured by answering 14 statements using a 4-point scale (1=Never True-4=Often True), indicating the degree of how much each statement applied to themselves in the past month. Examples are No matter what challenge I face, I always find a solution, I can handle unpleasant feelings, and I have realistic plans for the future. Identity Development will be assessed with a general self-esteem score as well as several measures to examine AMSMs sexual orientation and racial/ethnicity identity development that we have used in prior studies with YMSM of color. We will use the 10-item Rosenberg Self-Esteem, measured on 4-points (0=Strongly disagree-3=Strongly agree; .85). Sexual orientation identity will be assessed using Mayfields 23-item Internalized Homonegativity Inventory (IHNI), which uses a five-point scale (1=strongly disagree-5=strongly agree) to measure 3 subscales: Personal Homonegativity (11 items measuring negative emotions and attitudes towards ones own sexual orientation; .90), Gay Affirmation (7 items measuring positive attitudes and feelings that being gay is important, normal and fulfilling; ; .80), and Morality of Homosexuality (5 items measuring

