Over the first year of the study, we will adapt existing measures to ensure that they are developmentally appropriate for our participants through our Adolescent Development and Clinical Medicine Working Group and our Technical Expert Group. The Adolescent Development & Clinical Medicine Working Group will be led by [name] and will provide expertise regarding the psychosocial and clinical developmental milestones occurring during adolescence. Specifically, they will contribute to the adaptation of intervention measures and materials for early and middle-aged adolescents. The Working Group will include two leading HIV prevention and care clinicians who have devoted their career to the needs of AMSM, and two public health researchers, [name] and [name]. We have also convened a Technical Expert Group (TEG) who engage with youth and MSM in their roles as researchers ([name] & [name]), HIV and LGBTQ clinical and social service providers ([name]), national advocates invested in AMSMs well-being ([name] from NMAC & [name] from National Runaway Switchboard), and researchers who have experience in intervention/program development and evaluation with AMSM ([name]; [name]). The input of the TEG will be incorporated across all of our proposed activities, including reviewing the screening and assessment tools to ensure that they are culturally and linguistically appropriate for use with diverse groups of AMSM. Once we have reviewed our measures, we will pilot the HIPAA compliant online survey assessments to ensure that the survey layout works with different mobile devices (e.g., Android, iPhone) and browser platforms (e.g., Safari, Mozilla, Chrome, Explorer), that skip-patterns are correct, and that the server is saving the data appropriately. We have also taken several steps to ensure that the assessments are brief and also developmentally-appropriate. First, AMSM will not answer all listed constructs at every assessment. Identity-related constructs, for example, will be measured at 6-month intervals, whereas other constructs (e.g., comfort discussing sexuality) will be assessed at each follow-up. Second, consistent with best practices that we have used in prior HIV studies with pediatric and adolescent populations, we will use gate-keeping questions to decide whether participants should receive other probes within a domain. For example, a participant who has yet to become sexually active would receive cognitive assessments focused on HIV risk and awareness (e.g., attitudes, norms), but would not receive questions regarding behavioral intentions to engage in HIV prevention in next 3 months (e.g., HIV testing, PrEP) or questions regarding sexual risk behaviors (e.g., sexual behavior, HIV testing, PrEP use). Similarly, at each assessment, AMSM with no lifetime substance use will not be asked about additional substance use questions. Among sexually active participants, gate-keeping also provides opportunities to regulate how detailed the assessments will be. For example, we will assess sexual behaviors (yes/no) around kissing, touching, oral sex, vaginal and/or anal sex; if a participant notes only engaging in kissing and touching behavior, we will not ask any additional sexual behavior questions as they are not pertinent to HIV risk.

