Eligible individuals must (1) have been assigned a male sex at birth and identify as male at the time of enrollment into the study (cis-gender male), (2) be between the ages of 13 and 18 years (inclusive), (3) speak and read English, (4) report same-sex attractions and/or behaviors, (5) have access to the Internet, (6) live in one of the zip codes at least partially contained in the 109 counties included in the four regions selected for this trial, and (7) self-report as HIV-negative at time of enrollment.

Randomization and Blinding

Participants are randomized on a 1:1 basis using a stratified randomization by race and region. AMSM will be randomized to one of two arms, with 300 randomized to each arm (complete data on 250 AMSM per arm, allowing for attrition of 50 AMSM per arm).

Study Assessments

The proposed domains mirror the theoretical framework informing our intervention. We include a summary of the primary and secondary outcomes, key intervention mechanisms of change, and potential covariates. Assessments will not take more than 25 minutes to complete. We have taken several steps to ensure that the assessments are brief and developmentally appropriate. First, AMSM will not answer all listed constructs at every assessment. Identity-related constructs, for example, will be measured at 6-month intervals, whereas other constructs (e.g., comfort discussing sexuality) will be assessed at each follow-up. Second, consistent with best practices that we have used in prior HIV studies with pediatric and adolescent populations^{142,256}, we will use gate-keeping questions to decide whether participants should receive other probes within a domain. For example, a participant who has yet to become sexually active would receive cognitive assessments focused on HIV risk and awareness (e.g., attitudes, norms), but would not receive questions regarding behavioral intentions to engage in HIV prevention in next 3 months (e.g., HIV testing, PrEP) or questions regarding sexual risk behaviors (e.g., sexual behavior, HIV testing, PrEP use). Similarly, at each assessment, AMSM with no lifetime substance use will not be asked about additional substance use questions. Among sexually active participants, gatekeeping also provides opportunities to regulate how detailed the assessments will be.

Domain	Assessment time					
	Baseline	Month 3	Month 6	Month 9	Month 12	Month 15
Primary outcomes						
HIV knowledge	X		X		X	X
Condom use/communication efficacy	X		X		X	X

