HIV/STI testing	X		X		X	X
Outcomes required for analysis						
Demographics	X		X		X	X
Patient provider communication around sexual orientation		X		X		
Stigma		X		X		
Resilience		X		X		
Psychological needs	X		X		X	X
Future life goals		X		X		
Secondary outcomes						
Internalized homonegativity	X		X		X	X
PrEP use and willingness [X		X		X	X
Sex behaviors	X		X		X	X
Substance abuse	X		X		X	X
Depression	X		X		X	X
Anxiety	X		X		X	X
Self-Esteem	X		X		X	X
Covariates						
Peer influence		X		X		
Family support		X		X		
Discrimination		X		X		
Online behaviors		X		X		
Societal reaction to sexual orientation		X		X		
Ethnicity beliefs		X		X		
Relationship history	X		X		X	X
Intervention acceptability		X				

Sample Size

Our expected sample size for analyses across both conditions is N=600 (Intervention, n=300; Control, n=300), assuming a 15-20% loss to follow-up. We estimated the minimum detectable effect sizes at 80% power, for comparisons of the two groups for the continuous primary cognitive (e.g., behavioral intentions, attitudes, norms, self-efficacy) outcomes, as well as the difference in the proportion of AMSM who report increased behavioral in the outcomes (e.g., condom use, HIV testing) to engage in HIV prevention services and behaviors in our treatment arm vs. our attention-control arm. For mean differences, our sample size calculations are based on a two-sample t-test assuming equal variance using a two-sided significance of 0.05. At 80% power, we can detect a between-arm difference of $d=0.22$ at the final follow-up. For repeated measure analyses, assuming a within-person correlation of 0.25, we would be able to detect a difference of 0.08. A less favorable within-person correlation of 0.75 allows us to detect an effect size of 0.11. For proportions, our sample size calculations are based on a two-sample test of proportions using a two-sided significance of 0.05. To have 80% power to compare active treatment to the control group, we require at least 500 participants to find a 12.5% difference between treatment and control in cross-sectional analyses. Assuming within-person correlation of 0.25, we can detect an 8.8% difference. A less favorable within-person correlation of 0.75 allows us to detect an 11.3% difference.

Timing of Analyses

Final analysis will be conducted once the desired sample size is recruited has reached and completed the last study assessment.

Analysis Populations

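### Intention and sexual-risk items are withheld from youth not yet sexually active, but the stated detectable differences assume all 500 give data and no analysis set is defined for these outcomes

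*SAP*

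**What the plan says.** The gate is described in SAP, Study Assessments, and in Protocol, Methods, 2. Group Modifications. A participant not yet sexually active is asked about attitudes and norms but "would not receive questions regarding behavioral intentions to engage in HIV prevention in next 3 months". The same sentence withholds a second block of items: "or questions regarding sexual risk behaviors (e.g., sexual behavior, HIV testing, PrEP use". The protocol adds a further gate: "if a participant notes only engaging in kissing and touching behavior, we will not ask any additional sexual behavior questions". Both documents then describe a parallel gate for substance use, and here the timing is explicit: "Similarly, at each assessment, AMSM with no lifetime substance use will not be asked about additional substance use questions".

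Intentions have primary status in several places. Protocol, Study Design, says "The primary outcomes are cognitive (e.g., HIV prevention attitudes, norms, self-efficacy, behavioral intentions", and Study Procedures, 1. Detailed Description, repeats it. SAP, Endpoints, opens by naming confidence and HIV knowledge as primary, then describes intention subscales under the same heading. SAP, Sample Size, gives minimum detectable effects "for the continuous primary cognitive (e.g., behavioral intentions, attitudes, norms, self-efficacy) outcomes", and for proportions such as condom use and HIV testing. The stated values are d = 0.22 at final follow-up and 12.5 points with at least 500 participants.

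SAP, Randomization and Blinding, expects 250 of 300 per arm to have complete data. SAP, Analysis Populations, makes all randomised participants the primary population. SAP, Missing Data, deals with dropout and survey non-participation. Neither document gives the share expected to be sexually active, a scoring rule for items skipped by design, or the analysis set for gated outcomes.

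**The concern.** There are two separate consequences. First, an item that is not asked yields no value. A sample size that allows only for 15-20% loss to follow-up therefore overstates the information on intentions and on any behaviour outcome not derived for everyone.

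Second, becoming sexually active during 12 months of follow-up happens after randomisation. The SAP's opening rationale is that life-skills training may postpone the start of HIV risk factors, so an effect of iReach on who passes the gate is foreseeable. If the gate is re-applied at each survey, comparing the arms among those who pass it at month 6 or 12 is no longer a comparison of randomised groups. It could show a difference where there is none, or hide a real one.

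**Working it through.** **Inputs.** From SAP, Sample Size, and Randomization and Blinding: two-sided 0.05, 80% power, 1:1 allocation, 250 per arm with data. The share q of those 500 who pass the gate is not in the documents; I assume 0.3 to 0.7. No control rate is stated; I assume rates near 50%.

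**Reproducing the plan's figure for proportions.** With pooled variance and no continuity correction,

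n per arm = [1.960·√(2p̄(1−p̄)) + 0.842·√(p1(1−p1) + p2(1−p2))]² / (p2−p1)².

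- 43.75% v 56.25%: (1.960·0.7071 + 0.842·0.7016)² / 0.125² = 250 per arm, 500 in total.
- 50% v 62.5%: 247 per arm, 494 in total.

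So 500 for 12.5 points reproduces, provided all 500 give data.

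**Ungated value for means.** d = (1.960 + 0.842)·√(4/N) = 2.8016·√(4/500) = 0.25. The stated 0.22 does not follow from 250 per arm two-sided; it would need 325 per arm. That is a separate discrepancy, so 0.25 is the reference for the effect of gating.

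**Effect of the gate on N.** The same methods with N = 500q (d by noncentral t; proportions from 50%):

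| q | N with data | Detectable d | Detectable difference | Power for 50% v 62.5% |
|---|---|---|---|---|
| 1.0 | 500 | 0.25 | 12.4 points | 81% |
| 0.7 | 350 | 0.30 | 14.8 points | 66% |
| 0.5 | 250 | 0.36 | 17.4 points | 51% |
| 0.3 | 150 | 0.46 | 22.1 points | 34% |

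**Possible bias, with no true effect on intentions.** Suppose a share A = 40% is active under either arm and a further share C = 5-10% is active only under control. Let mean intentions in C differ from those in A by δ = 0.3-0.5 SD. All of these are assumptions. The control respondents are A plus C and the intervention respondents are A alone, so the false difference has size C/(A+C)·δ:

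- 0.05/0.45 · 0.3 = 0.033
- 0.05/0.45 · 0.5 = 0.056
- 0.10/0.50 · 0.3 = 0.06
- 0.10/0.50 · 0.5 = 0.10

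The range is 0.03-0.10 SD.

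**A second model as a check.** Assume 60% active under control and 50% under intervention, with correlation r = 0.3-0.5 between the propensity to be active and intentions. The mean propensity among the active is φ(z)/q, which is 0.644 at 60% and 0.798 at 50%. The false difference is r·(0.798 − 0.644) = 0.05-0.08 SD. With 150 and 125 respondents the type I error is about 7-10%. With equal shares active in the two arms, this model gives no bias.

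**The case against.** Several stronger readings are tempting, and the documents do not support them.

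- **That the trial's primary comparison is biased.** HIV knowledge, attitudes and norms are not gated, and self-efficacy is not named in the gate. The two outcomes that open SAP, Endpoints (confidence and knowledge) are therefore not clearly affected. The gate's examples for intentions are HIV testing and PrEP, so whether condom-use intentions are gated is not explicit either.
- **That the gate is certainly re-applied at each survey.** The explicit timing belongs to the substance-use gate. For sexual activity it is inferred from wording that describes a status able to change, and from the linking word between the two sentences. If status were fixed at baseline, the selection problem would go and the loss of N would stay.
- **That HIV testing is definitely restricted.** SAP, Endpoints, says the follow-up surveys repeat the testing questions and mentions no gate, which conflicts with Study Assessments. The schedule also lists testing among the primary rows, while Endpoints calls it secondary.
- **That the models drop inactive youth from behaviour outcomes.** The sexual-practices instrument asks first about partners and acts, so a count of condomless acts could logically be set to zero for someone not active. The SAP does not state that rule, and it does not state the opposite. Protocol, Methods, 1. Study Instruments, does frame the secondary outcomes among youth who engage in risk behaviours. For behaviours the fault is a missing definition, not a demonstrated bias.
- **That the whole gap from 0.22 to 0.30-0.46 is due to gating.** Part of it is there before any gating; the loss from gating runs from 0.25.

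What stands after these points: for gated intentions, the documents do not say who is analysed, and the stated detectable differences assume data that the survey design will not collect.

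**Conclusion.** The point holds and should be settled before the analysis. The stated detectable differences do not apply to gated intentions, or to behaviour outcomes unless these are defined for everyone. With 30-70% active, a share I have assumed, the detectable d is about 0.46-0.30 instead of 0.25, and the detectable difference in proportions is about 22-15 points instead of 12.5.

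The bias is conditional. It needs the gate to be re-applied during follow-up and iReach to change who becomes active or reports being active. Under the illustrative assumptions it is about 0.03-0.10 SD. With equal passage in both arms it largely disappears. Confidence is medium, because the active share and the timing of the gate both have to be assumed.

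**What to change.** 1. **Intentions.** Make the randomised comparison of gated intention items in participants already past the gate at baseline, and ask them the items at every scheduled wave. Define active so that it covers both the not-yet-active gate and the kissing-and-touching gate. Report later starters descriptively, and report gate passage by arm at each wave.
2. **Sexual behaviours.** Analyse all randomised participants, with outcomes defined for everyone: for example, any condomless sex in the past 3 months, with not active scored as no.
3. **HIV testing.** Reconcile SAP, Endpoints, with SAP, Study Assessments. Ask the test item of everyone, so that the tested-at-least-once analysis in SAP, Efficacy Analyses, covers all randomised participants.
4. **Sample size.** Restate the detectable differences for gated outcomes over a range of active shares, as in the table above.

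The cost is SAP wording, outcome derivation and one survey item asked of everyone. The downside is a smaller and less favourable stated N for intentions.
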